9.2 Serious Adverse Event

9.2.1 *Definition of Serious Adverse Event*

A Serious Adverse Event (SAE) is any untoward medical occurrence that at any dose (ICH E2A):

- Results in death
- Is life-threatening
- Requires in patient hospitalization or prolongation of existing hospitalization
- Results in persistent or significant disability / incapacity
- Is a congenital anomaly / birth defect
- Is an important medical event
- **Important medical event:** medical and scientific judgement should be exercised in deciding whether expedited reporting is appropriate in situations, such as important medical events that may not be immediately life-threatening or result in death or hospitalization but may jeopardize the patient or may require intervention to prevent one of the other outcomes listed in the definition above. These should also usually be considered serious.
Examples of such events are intensive treatment in an emergency room or at home for allergic bronchospasm; blood dyscrasias or convulsions that do not result in hospitalization; or development of drug dependency or drug abuse.
- **Life-threatening** in the definition of a serious adverse event refers to an event in which the patient was at risk of death at the time of the event; it does not refer to an event which hypothetically might have caused death if it were more severe.

| | | |
|--|--|----------------------------|
|  CONFIDENTIAL | Protocol No. GDX-44-016 Version No. 1.0 - ITA Date 15 March 2023 | F015919-05 Page 40 / 59 |
|--|--|----------------------------|

- **Hospitalization** refers to an admission and overnight stay at the hospital due to the adverse event. Emergency room visits that do not result in admission to the hospital should be evaluated for one of the other serious outcomes.

In case of a SAE, the investigator is responsible for the measures to be taken to ensure the safety of the trial patients.

Severe / Serious: the term “severe” is used to describe the intensity (severity) of a specific event (within the scale mild, moderate, severe). This is not the same as “serious”, which is based on patient event outcome or action criteria. The event itself may be severe but of relatively minor medical significance.

In this protocol, the following situations will not be considered as SAE, providing that they are clearly documented as such in the patient’s source data:

- Any hospitalization that had been planned before the trial and that will take place during the trial, provided there is no aggravation of the disease to which it is related.
- Hospitalizations, which are not associated to an adverse event (such as hospitalization for check-up).

9.2.2 ***Reporting Serious Adverse Events (SAE)***

All SAEs **must be reported immediately** by the investigator to Guerbet. Therefore, the investigator must immediately forward to Guerbet Pharmacovigilance department a duly completed report form for SAE, AESI or pregnancy (F001406) provided by Guerbet with trial documents, even if it is obvious that more data will be needed in order to draw any conclusion:

- **By e-mail to: [contact]**
- **Or by Fax #: [name]**

In case of emergency, Guerbet Pharmacovigilance department may be contacted at:

[name]

SAEs occurring at any time during the patient’s participation to the trial have to be reported also in medical file and in the appropriate section of the eCRF (see [section 9.1.2](#))

In order to allow the assessment and eventual subsequent regulatory reporting of the case, the following minimum information should be filled in:

- Patient’s details including age, sex and patient’s trial identification number
- Patient’s medical history relevant to the assessment of the event
- Type of event by reporting a diagnosis or if not available, symptoms
- Date and time to onset of the event
- End date of the event (will be reported in a follow-up report if the event is still ongoing at the time of initial notification)
- Date and time of investigational drug administration
- Seriousness criterion
- Causal relationship to the investigational drug or procedure (mandatory)
- Outcome at the time of reporting

If the investigator is aware of any new relevant information concerning a SAE (e.g.: outcome or any information that can have an impact on the assessment of the seriousness or the causal relationship between the SAE and the IMP), he has to send immediately to Guerbet Pharmacovigilance department the report form for SAE, AESI or pregnancy duly completed (F001406).

| | | |
|--|--|----------------------------|
|  CONFIDENTIAL | Protocol No. GDX-44-016 Version No. 1.0 - ITA Date 15 March 2023 | F015919-05 Page 41 / 59 |
|--|--|----------------------------|

In order to comply with current regulations as well as for comprehensive assessment purposes, additional information (e.g., autopsy results, biological values...) or clarifications may be required by Guerbet in a timely fashion to ensure accurate follow-up and assessment of each case and should be transmitted, anonymized, with a specific form (F018362) as soon as they are available.

SAEs should be followed up by the investigators until complete recovery of the patient or, if not possible, until stabilization of sequelae.

SAEs associated with trial procedures are to be notified using the same reporting procedure as described above.

According to local requirements, Guerbet or its representatives will communicate relevant safety information to the appropriate Agency(ies), Independent Ethics Committee (IEC) and/or all active investigators, as it becomes available.

The transmission of the information to Guerbet does not release the investigator from his responsibility to inform the regulatory authorities and or Independent Ethics Committee/ Institutional Review Board (IEC/IRB), if applicable.

9.3 Special situations

9.3.1 *Cases of overdose, lack of efficacy, interaction with drug or device, medication errors or misuses*

The safety information regarding the following special situations has to be collected and reported by the investigator with the same procedure as for AE, even if uneventful:

- Medication error: an unintended failure in the drug treatment process that leads to, or has the potential to lead to, harm to the patient (e.g.: wrong route of administration). A failure in the drug treatment process does not refer to lack of efficacy of the drug, rather to human or process mediated failures.
- Misuse: where the medicinal product is intentionally used not in accordance with the protocol.
- Occupational exposure to an IMP: an exposure to a medicinal product as a result of one's professional or non-professional occupation.
- Suspected drug-drug or drug device interaction with another product.
- Unusual Lack of efficacy: for Guerbet imaging products, lack of efficacy is mainly represented by cases of "lack of contrast " or " poor iconographic quality " or "no contrast" or "poor contrast" for MRI examinations.
- Overdose: administration of a quantity of a medicinal product given per administration or cumulatively which is above the maximum recommended dose, which is above 0,3 mmol/kg for the Elucirem® and Dotarem®.

9.3.2 *Pregnancy*

Any participating patient who becomes pregnant or, for a male patient, is aware of the pregnancy of his partner during the trial participation should inform immediately the investigational site. The female patient should immediately withdraw from the trial and must not receive any IMP.

| | | |
|--|--|----------------------------|
|  CONFIDENTIAL | Protocol No. GDX-44-016 Version No. 1.0 - ITA Date 15 March 2023 | F015919-05 Page 42 / 59 |
|--|--|----------------------------|

Any pregnancy (with or without an Adverse Event) of a woman participating in the trial that is discovered after the ICF signature must be reported to Guerbet Pharmacovigilance *via* the report form for SAE, AESI or pregnancy (F001406) (see [section 9.2.2](#)) unless the conception date is over 1 week after the last IMP administration. In this case, there is no need to report the pregnancy to Guerbet except in case of noxious effect related to the trial drug according to investigator's opinion.

Pregnancy will be monitored until delivery (health of infant up to 8 weeks of age) or early termination.

Specific forms "history and start of pregnancy" (F006030) and "course and outcome of pregnancy" (F006033) will be provided to the investigational sites by Guerbet Pharmacovigilance department. These forms will be used to collect information on the medical history of the pregnant woman and any risk factor of pregnancy complication, and on the follow-up and outcome of the pregnancy.

Any complication of pregnancy will be reported as an AE or SAE, as appropriate.

9.3.3 *Adverse Events of Special Interest*

An Adverse Event of Special Interest (AESI), serious or non-serious, is one of scientific and medical concern specific to the sponsor's product or programme, for which ongoing monitoring and rapid communication by the investigator to the sponsor can be appropriate. Such an event might warrant further investigation in order to characterize and understand it.

For Guerbet, the transmission of an AESI to the Guerbet Pharmacovigilance Department respects the same time frame as an SAE and should be reported using the report form for SAE, AESI or pregnancy (F001406).

The AESI for this protocol is the following: Nephrogenic Systemic Fibrosis (NSF). This disease affects the whole body (including kidney) but has its most prominent and visible effects in the skin, and mostly occurs in case of preexisting renal deficiency. NSF has been observed with gadolinium-based contrast agents, more frequently with the linear ones. The NSF has not been observed with Elucirem®, that is not a linear GBCA. In case of any suspicion of NSF, complementary investigation should be performed.

9.3.4 *Any suspicion of transmission of an infectious agent via an IMP*

Any suspicion of transmission of an infectious agent via an IMP should be considered as serious and processed as an SAE.

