1.2 Background

During the global clinical development program of Elucirem® nine studies were conducted since 2013. In total more than 1 065 patients/healthy volunteers were exposed to Elucirem® at different doses (up to 0.3 mmol/kg). A Phase IIb trial has been conducted in 280 adults with CNS diseases. This was a dose-response trial with a cross-over design allowing the comparison of contrast quality provided by each of the 4 tested gadopiclenol doses (0.025, 0.05, 0.1 and 0.2 mmol/kg) towards gadobenate dimeglumine at the dose of 0.1 mmol/kg. Elucirem® at 0.05 mmol/kg was identified as the lowest dose showing efficacy similar to the reference product [18]. In a randomized phase III trial including 256 randomized CNS patients, the non-inferiority of gadopiclenol at 0.05 mmol/kg compared to gadobutrol at 0.1 mmol/kg in terms of lesion visualization was demonstrated and a good safety profile was observed.

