3.2 Justification for dose

The safe and lowest effective clinical dose of gadopiclenol identified in phase IIb trial and confirmed by the results of the two phase III trials is 0.05 mmol/kg body weight. This dose will be used for gadopiclenol for this trial.

Dotarem® will be used, as an active comparator, at its standard approved dose of 0.1 mmol/kg BW.

| | | |
|--|--|----------------------------|
|  CONFIDENTIAL | Protocol No. GDX-44-016 Version No. 1.0 - ITA Date 15 March 2023 | F015919-05 Page 22 / 59 |
|--|--|----------------------------|

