5.1 Investigational Medicinal Product(s) Description

5.1.1 *Investigational Medicinal Product 1*

Name: Elucirem® (formulation G03277)

Pharmaceutical form: 20-mL vial containing 15 mL of solution presented as a sterile, clear, ready-to-use aqueous solution for injection.

Concentration: 0.5 M

Route and method of administration:

| | | |
|--|--|----------------------------|
|  CONFIDENTIAL | Protocol No. GDX-44-016 Version No. 1.0 - ITA Date 15 March 2023 | F015919-05 Page 25 / 59 |
|--|--|----------------------------|

Elucirem® will be intravenously (IV) administered at 0.05 mmol/kg using a power injector at the injection rate of minimum 4 mL/second followed by a 20-mL 0.9% saline flush at the same injection rate.

Preload bolus is allowed. If applied, the total dose (preload bolus + main bolus) of Elucirem® should not exceed 0.05 mmol/kg. The volume of the preload bolus, if any, should be collected in eCRF. Sufficient IMP must be allocated to one patient by IWRS.

Please refer to the Investigator Brochure for more information on Elucirem®.

5.1.2 *Investigational Medicinal Product 2*

Name: Dotarem® (gadoterate meglumine)

Pharmaceutical form: 20-mL vial containing 20 mL of solution presented as a sterile, clear, ready-to-use aqueous solution for injection.

Concentration: 0.5 M

Route and method of administration:

Dotarem® will be intravenously (IV) administered at 0.1 mmol/kg using a power injector at an injection rate of minimum 4 mL/second followed by a 20-mL 0.9% saline flush at the same injection rate.

Preload bolus is allowed. If applied, the total dose (preload bolus + main bolus) of Dotarem® should not exceed 0.1 mmol/kg.

Sufficient IMP must be allocated to one patient by IWRS.

Please refer to the SmPC for more information on Dotarem®.

5.1.3 *Precautions for use for both Investigational Medicinal Products*

Injection site tolerance

Caution during administration is necessary to avoid any extravasation. In case of extravasation, the injection must be stopped immediately. In case of local reactions, evaluation and treatment should be carried out as necessary.

Hypersensitivity

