5.6. Safety Evaluation

5.6.1. Extent of Exposure

The extent of exposure summary will be presented using the SS.

Duration (in days) between ICF signature and the IMPs administration, time from IMP administration to patient's last contact date, time from signature of ICF to patient's last contact date and time from MRI and histopathology will be tabulated by arm.

Descriptive statistics of the actual total volume (including the preload and main bolus) of IMPs will be presented by arm. Descriptive statistics of the actual volume of the preload bolus of IMPs will be presented by arm.

Occurrence of overdose (if any), actual injection rate of administration, brand of power injector used and volume of saline flush injected (if any) will be tabulated by arm.

Frequency tabulation of actual injection rate will be also displayed per arm according to following classes:

- ≥ 4 mL/s and ≤ 6 mL/s,
- > 6 mL/s.

Listing of extent of exposure and exposure will be presented in CSR appendix 16.2.1 and 16.2.7, respectively.

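### The 0.3 mmol/kg overdose threshold is unexplained against the trial doses, and no by-arm Safety Set summary shows dosing above the protocol figure

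*Protocol*

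**What the plan says.** Protocol 9.3.1 lists overdose among the special situations that sites must report, and defines it as a quantity, per administration or cumulative, "above the maximum recommended dose, which is above 0,3 mmol/kg for the Elucirem® and Dotarem". One figure serves both products.

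The dose sections give product-specific figures. Protocol 3.2 sets Elucirem at 0.05 mmol/kg and says "Dotarem® will be used, as an active comparator, at its standard approved dose of 0.1 mmol/kg BW". Sections 5.1.1 and 5.1.2 add that, if a preload is used, "the total dose (preload bolus + main bolus) of Elucirem® should not exceed 0.05 mmol/kg" and "the total dose (preload bolus + main bolus) of Dotarem® should not exceed 0.1 mmol/kg". Section 8.1.2 repeats both limits. The figure of 0.3 mmol/kg occurs in one other place, Protocol 1.2, where participants in the development programme "were exposed to Elucirem® at different doses (up to 0.3 mmol/kg".

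Overdose is recorded in the eCRF (Protocol 8.1.2). SAP 5.6.1 tabulates it by arm on the Safety Set, in the item "Occurrence of overdose (if any), actual injection rate of administration, brand of power injector used". The SAP gives no definition of its own.

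Actual and theoretical volume are compared in SAP 5.3.1, which plans counts of patients below, at and above the theoretical volume, a signed difference in mL and an unsigned relative difference. SAP 5.3 and Table 14.1.5.1 place these on the off-site PPS only. Protocol 11.3.5 had specified both PPS and Safety Set. SAP Table 3 makes a volume difference above 10% a major deviation, and SAP 5.2 removes patients with a major deviation from the PPS.

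**The concern.** The overdose row is the only planned by-arm output that labels excess dosing as such. If its threshold lies several multiples above the planned dose, the row will say little about whether patients received more gadolinium than the protocol intended. That matters here because Protocol 1.1 rests the trial on halving the gadolinium dose, and extending the Elucirem safety profile at 0.05 mmol/kg is a stated objective.

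One foreseeable slip shows the gap. Both products are 0.5 M, and the planned Dotarem volume per kg is twice that of Elucirem. Drawing up Elucirem at the Dotarem volume doubles the dose and still falls well short of the overdose threshold. The volume comparison that would show such a case with its direction is confined to an analysis set from which the case has been removed.

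**Working it through.** **Inputs.** Concentration 0.5 mmol/mL for both products; Elucirem "20-mL vial containing 15 mL of solution"; Dotarem "20-mL vial containing 20 mL of solution" (Protocol 5.1.1 and 5.1.2). Doses 0.05 and 0.1 mmol/kg. Threshold 0.3 mmol/kg (Protocol 9.3.1). Body weight of 70 kg is an assumption, with a range of 50 to 100 kg.

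**Reproducing the plan's own figure.** The 0.3 is a definition and cannot be derived. The theoretical volumes in SAP 5.3.1 can: dose / concentration gives 0.05/0.5 = 0.1 mL/kg for Elucirem and 0.1/0.5 = 0.2 mL/kg for Dotarem. Both match.

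**Threshold against trial dose.** 0.3/0.05 = 6 for Elucirem and 0.3/0.1 = 3 for Dotarem. As a volume, the threshold is 0.3/0.5 = 0.6 mL/kg for either product.

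**Weight below which k full vials exceed the threshold** = k × vial mL × 0.5 / 0.3.

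| | Elucirem (15 mL, 7.5 mmol) | Dotarem (20 mL, 10 mmol) |
|---|---|---|
| 1 vial | 7.5/0.3 = 25 kg | 10/0.3 = 33.3 kg |
| 2 vials | 15/0.3 = 50 kg | 20/0.3 = 66.7 kg |
| Weight covered by one vial at planned dose | 7.5/0.05 = 150 kg | 10/0.1 = 100 kg |

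**At 70 kg.** The threshold is 70 × 0.6 = 42 mL, against planned volumes of 7 mL and 14 mL. That is 42/15 = 2.8 Elucirem vials or 42/20 = 2.1 Dotarem vials, so a third vial would have to be opened for either product. One full Elucirem vial gives 7.5/70 = 0.107 mmol/kg, or 2.1 times the trial dose; one full Dotarem vial gives 10/70 = 0.143 mmol/kg, or 1.4 times. Over 50 to 100 kg a full vial gives 0.150 to 0.075 mmol/kg of Elucirem (3.0 to 1.5 times) and 0.200 to 0.100 mmol/kg of Dotarem (2.0 to 1.0 times). None of these exceeds 0.3.

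**Elucirem at the Dotarem volume.** 0.2 mL/kg × 0.5 = 0.1 mmol/kg, twice the trial dose and one third of the threshold. At 70 kg this is 14 mL, which one 15 mL vial can supply.

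**Where that patient would appear.** The relative volume difference is (14 − 7)/7 = 100%.

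- Overdose row, SAP 5.6.1: no.
- Table 14.1.5.1, off-site PPS: no, because above 10% is major under Table 3. At 70 kg the PPS keeps only differences up to 0.7 mL (Elucirem) or 1.4 mL (Dotarem).
- Deviation tables 14.1.2.1 and 14.1.2.2: yes, but the category combines too much with too little.
- Volume summary on the Safety Set, SAP 5.6.1: yes, but in mL, so body weight and dose are not separated.
- Listings 16.2.5.1 and 16.2.7.1: yes, as an individual record.
- Medication error or misuse report: yes if recognised, with no dedicated SAP output.

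**Rounding.** Protocol 5.6 rounds to whole mL. At 65 kg, 6.5 mL becomes 7 mL, and 7 × 0.5/65 = 0.054 mmol/kg. Correct rounding alone can therefore exceed 0.05, and any count of excess dosing must be taken against the rounded theoretical volume.

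**The case against.** The strongest reply is that these are different quantities. A maximum recommended dose used for safety reporting need not equal the dose under test, and the documents state no other maximum that would contradict 0.3. Product detail is deferred to the Investigator Brochure and the SmPC, which are not available here. This stands: a reader might infer an outright contradiction, but the text supports only an unexplained mismatch, clearest for Elucirem. Nor do the documents say that any dose above the trial dose is an overdose. That is a clinical decision, and the rounding example shows that the two figures cannot simply be equated.

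A reader might also infer that the overdose count is zero by construction. It is not. The eCRF records the number of vials, the IWRS may allocate more than one, and the definition covers cumulative dosing, so a multi-vial error could reach 0.3 mmol/kg.

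A third tempting reading is that over-dosing goes unrecorded, or that the SAP never shows its direction. Neither is right. The routes listed above capture the case, sites must document departures from theoretical volume, and SAP 5.3.1 does give direction. What the reply leaves unanswered is the analysis set: the directional comparison is shown only after patients more than 10% off volume have been removed.

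Finally, overdose is one item in an exposure table. The primary endpoint, margin, power and adverse event analyses are untouched, and nothing in the documents says that the count will be presented as evidence of safety.

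**Conclusion.** The point holds as a reporting gap. The 0.3 mmol/kg figure is unexplained and stands at 6 and 3 times the two trial doses. With one vial it can be exceeded only below 25 kg or 33.3 kg, and with two only below 50 kg or 66.7 kg, so the overdose count will probably be zero or near zero and would not register a doubled Elucirem dose.

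The firmer part is the departure from Protocol 11.3.5. Because the SAP drops the Safety Set from the volume comparison and Table 3 filters the PPS on volume, no by-arm Safety Set summary shows dosing above the protocol figure.

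This rests on the stated vial contents and concentration, and on the Table 3 classification surviving the data review meeting. The 70 kg examples use an assumed weight; the vial limits do not. How often excess dosing will occur cannot be judged from the documents.

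**What to change.** - **Protocol.** The sponsor should reconcile 9.3.1 with 1.2, 3.2, 5.1.1, 5.1.2 and 8.1.2, product by product, and state where 0.3 mmol/kg comes from. No threshold is proposed here. SAP section 4 suggests that recruitment may already be complete; if so, this becomes a documented explanation of the definition that sites applied.
- **SAP 5.3.** Present the 5.3.1 volume outputs on the Safety Set as well as the off-site PPS, as Protocol 11.3.5 states.
- **SAP 5.6.1 and Table 14.3.1.2.** Add, by arm on the Safety Set, the actual total dose in mmol/kg (actual volume × 0.5 / V2 weight) and the number of patients above the theoretical volume beyond whole-mL rounding. Label both as descriptive, and keep them apart from events meeting the 9.3.1 definition.

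Volume and weight are already collected, so the cost is a protocol clarification and a few extra table lines. Over-volume cases that would otherwise sit in listings become visible in a summary table.

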9.4 Other important safety issue / new fact

Any new data which may lead to a reassessment of the benefits / risks balance of the research or product being studied, changes in the use of that product, the conduct of the research or documents relating to the trial, or to suspend or interrupt or modify the protocol of the trial, or similar searches have to be evaluated by Guerbet.

It may include any new event likely to affect the safety of the patient's and that may be related to the conduct of the trial or the development of the trial drug such as:

- A SAE which could lead to the modification of the conduct of the trial (ex: SAE associated with the trial procedures),
- A new major finding from an animal study,
- A temporary halt of a trial for safety reasons if the trial is conducted with the same IMP in another country by the same sponsor,

| | | |
|--|--|----------------------------|
|  CONFIDENTIAL | Protocol No. GDX-44-016 Version No. 1.0 - ITA Date 15 March 2023 | F015919-05 Page 43 / 59 |
|--|--|----------------------------|

- Recommendations of the Safety Committee, where relevant for the safety of patients,
- Increase in the frequency of an expected event considered as clinically significant.

According to local requirements, Guerbet or its representatives will communicate relevant safety information to the appropriate Agency(ies), IEC/IRB and/or all active investigators, as it becomes available.

Consequently, this type of important safety issue might lead also to:

- Urgent safety measures and their notification
- Substantial trial documents modifications
- Premature discontinuation of the trial
- Premature discontinuation of the patient

